7.2. MULTICENTER STUDIES

This study will be conducted by multiple investigators at multiple sites in the US. No adjustment for geographic region is needed.

Center pooling will not be carried out for use in analyses for this study.

7.3. MISSING DATA

Missing safety data will not be imputed.

Missing efficacy data will be handled as described in Section 16.1.2 of this SAP.

Document:

\

Author:

Version Number:

Final 1.0

Version Date:

24FEB2020

Template No: CS_TP_BS016 Revision 4
Effective Date: 01Apr2016

Reference: CS_WI_BS005

For rating scales, such as SAPS-PD and CGI-S, unless otherwise specified, if any item score contributing to the total/subscale score is missing, then the total /subscale score will be set to missing.

7.4. MULTIPLE COMPARISONS/ MULTIPLICITY

There is only one primary efficacy comparison of change from baseline in SAPS-PD total score at Week 6. Therefore, no adjustment for multiplicity is planned in this study. For all other analyses, nominal p-values will be presented; no multiplicity adjustment will be performed.

7.5. EXAMINATION OF SUBGROUPS

Subgroup analyses will be conducted as stated in the respective efficacy and safety analysis sections. It should be noted that the study was not powered to detect treatment differences within subgroups.

The following subgroups will be assessed:

- Sex:
 - Female
 - Male
- Age group (years):
 - >=55 to <65
 - >=65 to <75
 - >=75
- Number of prior hospitalizations for PDP:
 - 0
 - 1
 - 2
 - 3 or more
- Duration of PDP (years):
 - < 5
 - >= 5 to < 10
 - >= 10 to < 20
 - >= 20
- Baseline MMSE (categories for subgroup analysis are different than subgroups presented for the demographic summaries, see Section 10):
 - >24
 - <=24

Document:

\

Author:

Version Number:

Final 1.0

Version Date:

24FEB2020

Template No: CS_TP_BS016 Revision 4
Effective Date: 01Apr2016

Reference: CS_WI_BS005

- Baseline NPI Hallucinations + Delusions (NPI [H+D]) Severity:
 - ≥ 6 to < 12
 - ≥ 12
- Lead-in Status:
 - Lead-in
 - Non Lead-in

8. OUTPUT PRESENTATIONS

APPENDIX 1 shows conventions for presentation of data in outputs.

The templates provided with this SAP describe the presentations for this study and therefore the format and content of the summary tables, figures and listings to be provided by IQVIA Biostatistics.

9. DISPOSITION AND WITHDRAWALS

All subjects who provide informed consent will be accounted for in this study.

For DB period, subject disposition will be presented for the SCR set and described by the randomized DB treatment group (where applicable) and overall for all subjects. The number and percentage of subjects who were screened, screen-failed, enrolled, randomized, received double-blind study medication, and completed or discontinued early from the DB treatment phase (including reasons for discontinuation), will be presented. The number of subjects who discontinued from the study before or at a given visit will be described by the treatment group and overall on the RND subjects.

For OL period, subject disposition will be presented for the RND set. The number and percentage of subjects who entered OL period, received at least one dose of OL study medication, and completed or discontinued early from the OL treatment phase (including reasons for discontinuation), will be presented. The number of subjects who discontinued from the study before or at a given visit will be described on the RND subjects.

Important protocol deviations (IPDs) will be identified and documented based on blinded reviews of data listings for DB period and on unblinded reviews of data listing for OL period. The IPD categories may include, but may not be limited to:

- Did not satisfy important inclusion, exclusion, and/or randomization criteria (DB period and Overall period)
- Received any disallowed concomitant medication
- Overall double-blind compliance rate $< 75\%$ or $> 125\%$ (DB period and OL period)

Document:

\

Author:

Version Number:

Final 1.0

Version Date:

24FEB2020

Template No: CS_TP_BS016 Revision 4
Effective Date: 01Apr2016

Reference: CS_WI_BS005

Further details on the identification of IPDs are provided in the Important Protocol Deviation Review Specifications document.

Individual IPDs will be presented for all randomized subjects in a data listing.

For the DB and OLE periods, IPDs will be identified for all randomized subjects and presented in data listings. The number and percentage of subjects within each IPD category will be summarized by treatment group and overall for the mITT populations.

10. DEMOGRAPHIC AND OTHER BASELINE CHARACTERISTICS

For DB period, demographic data and other baseline characteristics will be presented for the mITT population, safety population and PP population. For mITT and PP population, the data will be presented by randomized treatment groups and overall. For safety population, the data will be presented by the actual treatment received and overall. Basic demographic data will also be summarized for SCR population and for subjects enrolled by randomization status (i.e. randomized versus not randomized).

For OL period, demographic data and other baseline characteristics will be presented for the SAFOL population.

No statistical testing will be carried out for demographic or other baseline characteristics.

Categorical demography variables will be summarized by presenting the number and percentage subjects in each category. Continuous demography variables will be summarized using descriptive statistics (number of subjects, mean and standard deviation [SD], median, 25th percentile [Q1], 75th percentile [Q3], minimum, and maximum). The following demographic and other baseline characteristics will be reported for this study:

- Age (years) - calculated relative to date of informed consent, as a continuous variable and categorically:
 - >=55 to <65
 - >=65 to <75
 - >=75
- Sex
 - Female
 - Male
- Race
 - American Indian or Alaska Native
 - Asian
 - Black or African American
 - Native Hawaiian or Other Pacific Islander
 - White
 - Multiracial
 - Other

Document:

\

Author:

Version Number:
Version Date:Final 1.0
24FEB2020Template No: CS_TP_BS016 Revision 4
Effective Date: 01Apr2016

Reference: CS_WI_BS005

- Ethnicity
 - Hispanic or Latino
 - Not Hispanic or Latino
- Weight (kg) as a continuous variable
- Height (cm) as a continuous variable
- BMI (kg/m²), as a continuous variable and categorically:
 - Underweight: <18.5
 - Normal: 18.5 to <25.0
 - Overweight: 25.0 to <30.0
 - Obese: >=30.0
- Baseline SAPS-PD total score, SAPS-PD Hallucinations subscale score, SAPS-PD Delusions subscale score as continuous variables and categorically:
 - < Overall median value at baseline
 - >= Overall median value at baseline

Note: Median value for the above categories is based on subjects from the SAF population.
- Baseline NPI total score and NPI subscale scores (Hallucinations, Delusions, Agitation, Depression, Anxiety, Hallucinations + Delusions [H+D]) as continuous variables and NPI (H+D) score categorically:
 - >= 6 to < 12
 - >=12
- Baseline MMSE Score:
 - <=16
 - 17-19
 - 20-24
 - 25-27
 - 28-30
- Baseline CGI-S score, as a continuous variable and categorically:
 - < 4
 - >= 4

Weight, BMI, Baseline SAPS-PD and Baseline CGI-S for OL is defined as the last nonmissing value

Document: \

Author:

Version Number:

Final 1.0

Version Date:

24FEB2020

Template No: CS_TP_BS016 Revision 4
Effective Date: 01Apr2016

Reference: CS_WI_BS005

prior to the first dose of study drug in OL period.

The following psychiatric history data will be summarized only for DB period for the mITT population, safety population, and PP population in a separate table.

- Time since initial onset of PDP, in years, calculated relative to date of informed consent; both as a continuous variable and categorically (See APPENDIX 2 for partial date imputation rules for initial onset of PDP)
 - < 5
 - ≥ 5 to < 10
 - ≥ 10 to < 20
 - ≥ 20
- Number (0, 1, 2, 3 or more) of prior hospitalizations for treatment of PDP.

10.1. DERIVATIONS

- Time since initial onset of Parkinson disease (years):
$$(\text{Date of informed consent} - \text{date of initial onset of PD+1}) / 365.25$$
- Time since initial onset of PDP (years):
$$(\text{Date of informed consent} - \text{date of initial onset of PDP+1}) / 365.25$$
- BMI (kg/m^2) = weight (kg)/height (m)
2

11. MEDICAL AND SURGICAL HISTORY

Medical and surgical history information, including both past and concomitant medical conditions and major surgical history, as collected on the Medical History CRF form, will be coded using Medical Dictionary for Regulatory Activities (MedDRA), Version 19.0 or higher, and presented for DB period by treatment group for the safety population by System Organ Class (SOC) and Preferred Term (PT).

12. MEDICATIONS

Medications will be presented for double-blind period and open label-period based on the double-blind safety population and open-label safety population respectively and coded using the WHO drug dictionary, Version 01JUN2016E or higher.

Whenever available, the time information should be accounted for in the derivation of prior, concomitant, and post-treatment medications. See APPENDIX 2 for the handling of partial dates for medications. In the case where it is not possible to define a medication as prior, concomitant, or post-treatment, the

Document:

\

Author:

Version Number:
Version Date:Final 1.0
24FEB2020Template No: CS_TP_BS016 Revision 4
Effective Date: 01Apr2016

Reference: CS_WI_BS005

medication will be classified by the worst case; i.e. concomitant.

For DB period,

- Prior medications are medications which stopped prior to the first dose of DB study medication.
- Summary of antipsychotic use prior to screening (total and %), by type: nuplazid, quetiapine (Seroquel), clozapine, other
- Concomitant medications are medications which started at the same time of or after the first dose of DB study medication and at the same time of or before the last dose of DB study medication; or started prior to and ended at the same time of or after the first dose of DB study medication; or started at the same time of or prior to the last dose of DB study medication and marked as ongoing.
- Post-treatment medications are medications which started after the last dose of DB study medication.

For OL period,

- Prior medications are medications which stopped prior to the first dose of OL study medication.
- Concomitant medications are medications which started at the same time of or after the first dose of OL study medication and at the same time of or before the last dose of OL study medication; or started prior to and ended at the same time of or after the first dose of OL study medication; or started at the same time of or prior to the last dose of OL study medication and marked as ongoing.
- Post-treatment medications are medications which started after the last dose of OL study medication.

Prior and concomitant medication use will be summarized by Anatomical Therapeutic Chemical (ATC) Level 3 classification and preferred name using frequencies and percentages. Prior, concomitant, and post-treatment medications will be provided in data listings.

13. STUDY MEDICATION EXPOSURE

Duration of exposure to study medication will be summarized for the safety population.

Interruptions, compliance, and dose changes are not taken into account for duration of exposure.

Duration (in days) of exposure will be summarized both as a continuous variable for double-blind treatment period and open-label extension period, and categorically:

For double-blind:

Document:

\

Author:

Version Number:
Version Date:

Final 1.0
24FEB2020

Template No: CS_TP_BS016 Revision 4
Effective Date: 01Apr2016

Reference: CS_WI_BS005

- Number and percentage of subjects with drug exposure ≥ 1 , ≥ 4 , ≥ 7 , ≥ 14 , ≥ 21 , ≥ 28 , ≥ 35 , and ≥ 42 days;
- Number and percentage of subjects with drug exposure for 1 - 3, 4 - 6, 7 - 13, 14 - 20, 21 - 27, 28 - 34, 35 - 41 and ≥ 42 days.

For open-label:

- Number and percentage of subjects with open-label extension study drug exposure ≥ 1 , ≥ 7 , ≥ 14 , ≥ 21 , ≥ 28 , ≥ 56 , and ≥ 84 days;
- Number and percentage of subjects with extension study drug exposure for 1 - 6, 7 - 13, 14 - 20, 21 - 27, 28 - 55, 56 - 83 and ≥ 84 days.

The modal daily dose during the double-blind period and the open-label period (i.e. the dose level that a subject was on for the most number of days during the study) will be summarized categorically by treatment group:

- o 25 mg/day
- o 50 mg/day
- o 75 mg/day
- o Tie between 25 mg/day and 50 mg/day
- o Tie between 25mg/day and 75 mg/day
- o Tie between 50mg/day and 75 mg/day
- o Tie between 25mg/day, 50 mg/day, and 75 mg/day

Include histogram showing distribution of each dose by visit. Include linear plots for each subject showing dose taken over time.

For DB period, the number of days that a subject was on the 25 mg/day dose level, on the 50 mg/day dose level and on the 75 mg/day dose level will also be summarized, both as a continuous variable and categorically:

- o 1 - 3 days
- o 4 - 6 days
- o 7 - 13 days
- o 14 - 20 days
- o 21 - 27 days
- o 28 - 34 days
- o 35 - 41 days
- o ≥ 42 days

For OL period, the number of days that a subject was on the 25 mg/day dose level, on the 50 mg/day dose level and on the 75 mg/day dose level will also be summarized, both as a continuous variable and categorically:

- o 1 - 6 days
- o 7 - 13 days
- o 14 - 20 days

Document:

\

Author:

Version Number:

Final 1.0

Version Date:

24FEB2020

Template No: CS_TP_BS016 Revision 4
Effective Date: 01Apr2016

Reference: CS_WI_BS005

- 21 – 27 days
- 28 – 55 days
- 56 – 83 days
- ≥ 84 days

Mean daily dose will be calculated for the DB period and entire open-label extension period as the cumulative dose (mg) of SEP-363856 divided by the duration of exposure (in days), where cumulative dose is the sum of all doses a subject received during the DB period or open-label extension period. Modal daily dose will be determined as the daily dose that is taken for the most time (in terms of number of days) among all doses taken during the DB or OL extension period. Both mean daily dose and modal daily dose will be summarized.

The dose adjustment decision at each visit will be summarized in a shift table for DB and for OL extension period, for the mITT and safety populations.

13.1. DERIVATIONS

- Duration of exposure (in days) will be calculated as:

last dose date – first dose date + 1

For double-blind period, first dose date and last dose will be taken from the eCRF “Study Drug Administration / Drug Accountability - Double Blind” form.

For open-label period, first dose date will be taken from the eCRF “Study Drug Administration / Drug Accountability – Open-label” form. Last dose date will mainly be taken from the EX/DA page, which should match the eCRF “End of Study” form.

14. STUDY MEDICATION COMPLIANCE

Compliance to study medication will be summarized for the safety population by treatment group and overall for DB period. Compliance to study medication will be summarized for the open-label safety population for OL extension period.

Percent compliance will be calculated by visit and overall for the double-blind and open-label period.

Non-compliance is defined as less than 75% or more than 125% non-missing compliance for the double-blind period and OL extension period. Subjects with missing compliance will not be classified as non-compliant.

Compliance will be summarized both as a continuous variable (i.e. mean percentage) and categorically (i.e. number and percentage of subjects who are compliant vs. non-compliant, or with compliance < 75%, 75% - 125%, > 125%, and missing).

Document:

\

Author:

Version Number:

Final 1.0

Version Date:

24FEB2020

Template No: CS_TP_BS016 Revision 4
Effective Date: 01Apr2016

Reference: CS_WI_BS005

14.1. DERIVATIONS

Compliance with study medication will both be calculated for each period defined by study visits (i.e. per-visit compliance) and overall.

Per-visit compliance for the period defined by visit (V-1) and visit V will be calculated as:

$$\frac{\# \text{Capsules dispensed at Visit (V-1)} - \# \text{Capsules returned at Visit V} - \# \text{Capsules reported lost during this period}}{\# \text{Capsules should be taken per day} \times (\text{Date of Visit V} - \text{Date of Visit (V-1)})} \times 100\%$$

One capsule per day are supposed to be taken. If any of the following numbers are missing, per-visit compliance will not be calculated for the period impacted: number capsules dispensed at Visit (V-1), number capsules returned at Visit V, and number capsules reported lost during this period.

If a subject discontinued from the study in between Visit (V-1) and Visit V, then the above formula will be modified to:

$$\frac{\# \text{Capsules dispensed at Visit (V-1)} - \# \text{Capsules returned at Visit ET} - \# \text{Capsules reported lost during this period}}{\# \text{Capsules should be taken per day} \times (\text{Date of Visit ET} - \text{Date of Visit (V-1)})} \times 100\%$$

The per-visit compliance calculated above will contribute to the summary of per-visit compliance for the period defined by visit (V-1) and visit V.

Overall compliance will be calculated as:

$$\frac{\text{Total } \# \text{capsules dispensed} - \text{Total } \# \text{capsules returned} - \text{Total } \# \text{capsules reported lost}}{\# \text{Capsules should be taken per day} \times \text{Duration of Exposure}} \times 100\%$$

Duration of exposure is calculated as specified in Section 14.1.

If any of the following numbers are missing at one or more visits, overall compliance will not be calculated: number capsules dispensed, number capsules returned, number capsules reported lost.

15. EFFICACY OUTCOMES

In addition to the analyses described in Sections 15.1.3, 15.1.4, 15.2.3, 15.3.3, all efficacy variables will be summarized descriptively by treatment group and visit (including the Week 6 LOCF endpoint) for the mITT population. For SAPS-PD total score and CGI-S score, the data will also be summarized descriptively for each subgroup.

15.1. PRIMARY EFFICACY

15.1.1. PRIMARY EFFICACY VARIABLE & DERIVATION

The primary efficacy variable is the change from baseline in SAPS-PD total score at Week 6 in DB period for testing superiority of SEP-363856 to placebo.

Document:

\

Author:

Version Number:
Version Date:Final 1.0
24FEB2020Template No: CS_TP_BS016 Revision 4
Effective Date: 01Apr2016

Reference: CS_WI_BS005

SAPS-PD is a Parkinson's disease-adapted subset of nine items derived from the Scale for Assessment of Positive Symptoms (SAPS), including seven items assessing individual symptoms (four items for hallucinations and three items for delusions), a global hallucinations item and a global delusions item. Separate items are rated from 0 (absent) to 5 (severe), for a total possible score on the SAPS-PD ranging from 0 to 45. Total score will be equal to the sum of the seven items plus the global hallucinations, plus the global delusions.

The SAPS-PD subscale for hallucinations is defined as the sum of the 4 items for hallucinations and the global hallucination item. The SAPS-PD subscale for delusions is defined as the sum of the three items for delusions and the global delusion item.

There can be three different SAPS-PD item results: "Original" SAPS-PD item result, "Review" SAPS-PD item result, and "Consensus" SAPS-PD item result. When calculating the SAPS-PD total score or subscale scores, the following rule will be used when selecting individual items to calculate the total score or subscale scores:

- 1) Select the "Consensus" item result when available.
- 2) If the "Consensus" item result is not available, then select the "Original" item result. The "Review" item score should never be used to calculate the SAPS-PD total score or subscale scores.

The choice of "Consensus" or "Original" item result is selected independently for each of the seven items from the SAPS-PD questionnaire.

For the above total score and subscale scores, if any item contributing to its calculation is missing then the score will be set to missing. Only subjects on-period data will be taken into account in this analysis (see Section 6.9)

15.1.2. MISSING DATA METHODS FOR PRIMARY EFFICACY VARIABLE(S)

The SAPS-PD total score will be set to missing if any one item is missing. The primary efficacy variable, change from baseline in SAPS-PD total score at Week 6, will be set to missing if SAPS-PD total score at Week 6 is missing. The same applies to all other visits.

The primary analysis of the primary efficacy variable will use a mixed model for repeated measures (MMRM) based on observed data (with early termination data mapped as described in Section 6.4). Missing data will not be imputed.

The analysis of covariance (ANCOVA) of the primary efficacy variable will utilize the Week 6 LOCF endpoint as sensitivity analysis, which is imputed as described in Section 6.3.

15.1.3. PRIMARY ANALYSIS OF PRIMARY EFFICACY VARIABLE(S)

The primary objective of this study is to test whether the mean changes from baseline in SAPS-PD total score at Week 6 in the SEP-363856 (25, 50 or 75 mg/day) group and the placebo group are equal.

Let μ_{SEP} and μ_{PBO} represent the mean changes from baseline at Week 6 in SAPS-PD total score for the SEP-363856 (25, 50 or 75 mg/day) and placebo groups, respectively. The following hypothesis will be tested:

Document:

\

Author:

Version Number:
Version Date:Final 1.0
24FEB2020Template No: CS_TP_BS016 Revision 4
Effective Date: 01Apr2016

Reference: CS_WI_BS005

H₀: $\mu_{\text{SEP}} = \mu_{\text{PBO}}$ versus **H₁:** $\mu_{\text{SEP}} \neq \mu_{\text{PBO}}$

The primary efficacy analysis will be performed on the mITT population.

Change from baseline in SAPS-PD total score at Week 6 will be analyzed using an MMRM model, with fixed factors for visit (Weeks 2, 3, 5 and 6; as a categorical variable), treatment, and treatment-by-visit interaction, and with baseline SAPS-PD total score as a covariate. An unstructured covariance matrix will be used to model the within-subject correlation. The Kenward-Roger approximation will be used to calculate the denominator degrees of freedom.

In case the model above fails to converge, a spatial exponential covariance structure and a spatial power covariance structure will be assumed sequentially. The first covariance structure to yield convergence will be used in the analysis.

Within group effect size at each time point will be calculated as the least squares (LS) mean of each treatment group divided by the model estimate of standard deviation, obtained as the square root of the corresponding diagonal element of the residual covariance matrix (R matrix from PROC MIXED).

Between group effect size at each time point will be calculated as the LS mean difference divided by the model estimate of standard deviation, obtained as described above.

LS means (\pm SE) of change from baseline in SAPS-PD total score will be plotted by week and treatment group.

The above analysis will also be performed on the SAPS-PD subscale score for hallucinations and the SAPS-PD subscale score for delusions.

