- Blood samples for clinical laboratory evaluation (hematology, serum chemistry, serum prolactin, HbA_{1c}, glucose panel, and lipid panel)
- Perform breath alcohol test
- If subject and caregiver signed separate genetic informed consent, collect blood samples for pharmacogenomics (CYPP450 2D6)
- Urine sample for urinalysis
- Blood sample for determination of plasma SEP-363856 and SEP-363854 (predose, and 1 sample between 1-3 hours post dose)
- SAPS-PD
- NPI
- CGI-S
- MMSE

- UPDRS II and UPDRS III
- SCOPA-DS
- SCOPA-NS
- RBDQ
- C-SSRS
- Adverse events
- Review randomization criteria
- Randomize to treatment
- Dispense study drug
- Administer first study drug dose

After receiving the initial dose, subjects will remain in the clinic for at least 2 hours of clinical observation, which will include periodic assessments of orthostatic vital signs (1 hour [\pm 15 min] and 2 hours [\pm 15 min] post dose); additional medical assessments can be performed as needed per investigator discretion. Findings will be collected on appropriate case report forms (CRFs). Subjects will be discharged home if medically stable. Telephone calls to the subjects will be made on the first 2 days following the visit (see Section 11.9.11).

If subject appears to be symptomatic as assessed by the site during a telephone contact and requires additional assessments in-clinic, an unscheduled visit will be made as early as possible (see Section 11.9.12).

11.9.3. Visit 4 (Day 8 ± 2 days), Visit 5 (Day 15 ± 2 days), and Visit 6 (Day 29 ± 2 days)

The following procedures will be conducted during each visit (unless otherwise specified):

- Prior/concomitant medications
- Study drug accountability
- Dispense study drug
- Vital sign measurements (including orthostatic effects)
- SAPS-PD
- NPI (Visit 5 only)
- CGI-S (Visit 5 only)
- MMSE (Visit 5 only)
- UPDRS II and UPDRS III
- SCOPA-DS (Visit 5 only)
- SCOPA-NS (Visit 5, only)
- RBDQ (Visit 5, only)

- C-SSRS
- Adverse events

If the subject titrates up, the subject will remain in the clinic for at least 2 hours of clinical observation, which will include periodic assessments of orthostatic vital signs (1 hour [\pm 15 min] and 2 hours [\pm 15 min] post dose); additional medical assessments can be performed as needed per investigator discretion.

Telephone calls to the subjects will be made on the first 2 days after a dose adjustment (increase or decrease) (see Section 11.9.11).

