5.4. MODIFIED INTENT-TO-TREAT [mITT] POPULATION

The modified intention-to-treat (mITT) population is defined as all subjects who were randomized, received at least one dose of study drug, and had a baseline and at least one post-baseline total score in SAPS-PD or NPI or CGI-S during the DB treatment period.

The mITT population will be the primary population for the efficacy analyses. Subjects will be analyzed according to randomized treatment group.

5.5. mITT COMPLETE CASES [mITTComp1] SAPS-PD POPULATION

The mITT complete cases (mITTComp) is defined as all subjects of the mITT who completed SAPS-PD assessment at the Week 6 visit (Visit 7 not including the ET visit), and have Baseline and Week 6 SAPS-PD total score data available. If a subject had missing SAPS-PD data at visits other than Week 6 (i.e. Visits 3 [Week 1], Visit 4 [Week 2], Visit 5 [Week 3], or Visit 6 [Week 5]), or if he had missing data in assessments other than SAPS-PD at Week 6 (Visit 7), this subject will still be included in the complete case analysis for SAPS-PD total score. Week 6 visit is defined in the protocol as study visit day 43 (+/-2 days). The mITT Complete cases population will be reviewed in a similar manner as the Per-Protocol population as some subjects may have performed a Week 6 visit outside of the visit window but they are still completers.

5.6. mITT COMPLETE CASES [mITTComp2] CGI-S POPULATION

Same as mITTComp1, for CGI-S instead.

The mITTComp1 and mITTComp2 populations will be used for the complete case analysis of the SAPS-PD total score and CGI-S score respectively. Subjects will be analyzed according to randomized treatment group.

Document:

\

Author:

Version Number:
Version Date:Final 1.0
24FEB2020Template No: CS_TP_BS016 Revision 4
Effective Date: 01Apr2016

Reference: CS_WI_BS005

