6.6. STATISTICAL TESTS

All statistical inference, unless otherwise stated, will be performed with 2-sided tests at the significance level of 0.05 and 2-sided 95% confidence intervals (CIs), unless otherwise specified in the description of the analyses.

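### The two fallback covariance structures for the primary MMRM are one and the same constant-variance model, so a failed unstructured fit would leave a Week 6 standard error that is wrong whenever variance differs between visits (minor)

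*SAP*

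**What the plan says.** SAP 15.1.3 models change from baseline in SAPS-PD total score with "fixed factors for visit (Weeks 2, 3, 5 and 6; as a categorical variable), treatment, and treatment-by-visit interaction", plus baseline score. The main specification is: "An unstructured covariance matrix will be used to model the within-subject correlation". If that model does not converge, "a spatial exponential covariance structure and a spatial power covariance structure will be assumed sequentially", and the choice between them is mechanical: "The first covariance structure to yield convergence will be used in the analysis". Inference is model-based: "The Kenward-Roger approximation will be used to calculate the denominator degrees of freedom". No sandwich standard error is named. Under SAP 6.6, inference "will be performed with 2-sided tests at the significance level of 0.05".

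The same section standardises the effect size at each visit by that visit's diagonal element of the residual covariance matrix. Appendix 3 codes only the unstructured model. No distance variable is named for the spatial structures, and the visit variable in Appendix 3 is numbered 4 to 7. Protocol 15.3.5.1 specifies the unstructured matrix and no fallback.

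**The concern.** A sequence of fallbacks is useful only if a later entry differs from the one that failed. Here the two entries are algebraically the same, so the plan has one fallback written as two.

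That one fallback also drops the feature of the unstructured model that matters most for a single-visit contrast, namely a variance estimated for that visit. The Week 6 standard error would rest on a variance pooled over all four visits. If the SD of change grows over time, the standard error is too small and the primary p-value too optimistic. If the SD shrinks, the test is conservative. The visit-specific effect-size standardiser would collapse to a single value.

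The model is reused for both SAPS-PD subscales, the multiply imputed datasets, and the complete-case and per-protocol analyses. Similar models serve CGI-S, NPI and MMSE, and the subgroup models add three-way interactions. The fallback sentence could therefore be called on in more than one place.

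**Working it through.** **Inputs from the documents.** 36 subjects, 24 versus 12 (SAP 3.4). Four post-baseline visits: "Visit 4 (Day 8 ± 2 days), Visit 5 (Day 15 ± 2 days), and Visit 6 (Day 29 ± 2 days") in Protocol 11.9.3, and for the last, "Week 6 visit is defined in the protocol as study visit day 43 (+/-2 days") in SAP 5.5. The gaps between visits are therefore 7, 14 and 14 days. Two-sided alpha is 0.05. The documents give no SAPS-PD SD at any visit, so every SD pattern below is an assumption.

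**The plan's own figure.** The plan gives no number for the fallback. Its only related figure is power, which reproduces: a noncentral t with 34 df and noncentrality d × sqrt(24 × 12 / 36) gives 59.4%, 48.6%, 37.8% and 28.0% for d = 0.8, 0.7, 0.6 and 0.5. The stated values are 59%, 48%, 37% and 27%.

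**Step 1, identity.** Spatial exponential: s² × exp(-d/theta). Spatial power: s² × rho^d. Since exp(-d/theta) = [exp(-1/theta)]^d, setting rho = exp(-1/theta) makes them equal at every distance, whatever distance variable is used. Fitting both by REML to one simulated trial gave rho 0.84308, variance 0.74083 and -2 REML log-likelihood 30.91798 in both cases.

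**Step 2, effect on the Week 6 standard error.** With complete data the true standard error is approximately SD(Week 6) × sqrt(1/24 + 1/12). The fallback in effect replaces the Week 6 variance by roughly the mean of the four visit variances. Large-sample type I error is then

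2 × [1 - Phi(1.96 × sqrt(mean visit variance / Week 6 variance))].

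For SDs 4/5/6/7: mean variance = (16 + 25 + 36 + 49)/4 = 31.5; ratio = 31.5/49 = 0.643; square root 0.802, so the standard error is about 20% too small; type I error 11.6%.

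**Step 3, simulation.** Null trials used 24 versus 12 subjects on Days 8/15/29/43, the SAP fixed effects and a REML fit of the spatial model. The main run had 2,000 trials per scenario, with Satterthwaite df standing in for Kenward-Roger. The ranges also include smaller or independent repeats of the same scenarios.

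| Assumed SD, Weeks 2/3/5/6 | Week 6 / Week 2 | Variance ratio | Formula | Simulated, complete data | Simulated, 15% random dropout |
|---|---|---|---|---|---|
| 6/6/6/6 | 1.0 | 1.000 | 5.0% | 5.2-5.5% | 5.1% |
| 5/5.5/6/6.5 | 1.3 | 0.790 | 8.2% | 7.2-8.7% | 6.9% |
| 4/5/6/7 | 1.75 | 0.643 | 11.6% | 9.6-10.8% | 10.9% |
| 3/4/6/7 | 2.33 | 0.561 | 14.2% | 13.5-13.8% | not run |
| 7/6/5/4 | 0.57 | 1.969 | 0.6% | 0.7-1.2% | not run |

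A further pattern, 3/4/6/7.5 (2.5-fold), gave 13.7% in simulation. In the main run, a Week 6 ANCOVA, which uses only the Week 6 variance, stayed between 4.6% and 5.7% in every scenario.

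**Step 4, is rising variance plausible?** Raw scores with constant variance and autoregressive correlation of 0.90 or 0.95 per week, analysed as change from baseline, gave 11.7% and 10.1%. That assumes no measurement error. With raw-score reliability of 0.7-0.8 (an assumption) and weekly autocorrelation of 0.90-0.98, the formula gives SD ratios of 1.08-1.30 and type I error of 5.9-8.1%. At reliability 0.9 it gives 8.2-9.5%.

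**Step 5, do heterogeneous-variance structures repair it?** For 5/5.5/6/6.5, heterogeneous AR(1) and compound symmetry gave 4.4-5.8% over two runs (800 and 1,000 trials, 33 df), and heterogeneous Toeplitz gave 4.4% in the second. For 4/5/6/7, all three gave 4.2% in 1,000 trials, against 9.6% for the SAP fallback in the same run.

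**Step 6, how often would the fallback be used?** The unstructured model has 4 variances and 6 covariances, 10 parameters in 36 subjects. It was fitted to 100 simulated trials at each of 0%, 15%, 30% and 40% monotone dropout (SDs 4/5/6/7). There were no failures or near-singular fits in 400 trials, so the upper 95% bound is about 3/400 = 0.75%. This used Gaussian data, random dropout and a general-purpose optimiser, not PROC MIXED on real SAPS-PD scores.

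**The case against.** The strongest reply is that the sentence will probably never be used. The unstructured fit did not fail in 400 simulated trials, so averaged over the whole procedure the type I error of the primary test hardly moves. This stands, within the limits of that simulation, and it is the main reason to rate the point as minor. The inflation figures also come from fitting the spatial model to all simulated trials. The error rate conditional on an actual unstructured failure was not estimated.

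The size depends on assumed SDs. A modest rise costs two to four percentage points, constant SD costs nothing, and falling SD makes the test conservative. This stands too.

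SAP 15.1.4.4 already plans a Week 6 LOCF ANCOVA, whose residual variance comes from the Week 6 endpoint alone. A p-value driven by too small a spatial standard error would look out of line beside it. This is partial cover: the ANCOVA is a sensitivity analysis and carries the weaknesses of LOCF.

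Spatial structures respect the unequal 7/14/14-day gaps, whereas heterogeneous Toeplitz and AR(1) go by visit order. That is a genuine trade-off. The heterogeneous Toeplitz model also still needs 7 parameters.

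Two stronger readings are tempting. One is that the second fallback is void; the two parametrisations can behave differently in an optimiser, so it may rescue a fit numerically, although it cannot offer another model. The other is that the plan doubles its type I error at Week 6. The documents do not support this: it would need both a failed unstructured fit and a rise in SD of roughly 1.75-fold or more, and they give no SDs by visit.

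**Conclusion.** The structural point is exact and rests on no assumption: spatial exponential followed by spatial power is one model with one variance for all visits.

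Its consequence is conditional. If the unstructured fit fails, Week 6 type I error ranges from about 1% to 14% over the SD patterns examined, against a nominal 5%. It is about 5% for constant SD, 7-9% for a 1.3-fold rise, 10-14% for a 1.75- to 2.5-fold rise, and about 1% for a fall. The direction therefore depends on data that the documents do not contain. These figures assume normal data, 24 versus 12 subjects, and complete data or 15% random dropout.

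In an exploratory Phase 2 trial, with a trigger that looks uncommon, this is a minor correction. It is worth making before unblinding, because a fallback is specified precisely so that nobody has to choose a structure after seeing the data.

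**What to change.** In SAP 15.1.3, replace the sentence on fallback structures with a sequence that allows a separate variance at each visit: heterogeneous Toeplitz (7 parameters), then heterogeneous AR(1) (5), then heterogeneous compound symmetry (5). Use the first that converges and keep Kenward-Roger. State that the same sequence applies wherever the primary MMRM is reused, and add the code to Appendix 3. If a spatial structure is kept as a last resort, list it once and name the distance variable as study day; the 4 to 7 visit numbering would treat the visits as equally spaced.

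The cost is one sentence and a few lines of code. The small statistical price is that heterogeneous Toeplitz and AR(1) ignore the unequal gaps between visits. If the unstructured model converges, no result changes.
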